5.3.3 Main Analytical Approach for Primary Estimand and Primary Endpoint

Primary study hypothesis

The primary efficacy analysis for this study will test the superiority of the active drug over the placebo at Week 116 with a two-sided test corresponding to the following null hypothesis, H_0 , and alternative hypothesis, H_1 :

$$H_0: \mu_{\text{active}} = \mu_{\text{placebo}}$$

$$H_1: \mu_{\text{active}} \neq \mu_{\text{placebo}}$$

Where μ_{active} and μ_{placebo} are the mean changes from baseline to Week 116 in the CDR-SB score for each arm.

Time Windowing

For the primary endpoint (and in general for clinical efficacy endpoints) the following time windows will be used for analyses (see [Table 4](#)), based on study days. Study days are defined based on days on study since the date of the first dose, with the day of the first dose being study day 1.

Table 4 Time windows for clinical endpoint assessments

| Visit | Target day | Time window (in study days*) |
|----------|------------|--|
| Baseline | 1 | Up to Day 35 |
| Week 24 | 169 | 72, 266 |
| Week 52 | 365 | 267, 448 |
| Week 76 | 533 | 449, 630 |
| Week 104 | 729 | 631, 770 |
| Week 116 | 813 | 771, earliest between 897 or first dose of OLE |

In cases where more than one assessment falls within a time window, the assessment with the date closest to the target day is selected whether it's a scheduled, unscheduled or an early termination visit.

With regards to an ICE of withdrawal from study treatment, an assessment will be regarded as having happened after the ICE of withdrawal from study treatment if it is collected >28 days since the last dose.

General strategy to address the ICEs

For the primary estimand, a treatment policy approach will be used for all SDCR ICEs. In line with the clinical question of interest, the aim is to estimate a treatment effect irrespective of the occurrence of these ICEs. This approach is largely in line with the EMA guideline on the clinical investigation of medicines for the treatment of AD ([EMA 2018](#)).

All NSDCR ICEs will be handled using a hypothetical approach. The aim is to estimate a treatment effect “as if” the ICE had not happened. Post-ICE outcome values compatible with a hypothetical strategy are not directly observable. Consequently, any observed outcome values after NSDCR ICEs will be removed and treated as missing data for analysis purposes.

For participants with multiple ICEs, the type of the first ICE will determine the strategy to be considered.

Missing data assumptions for the primary estimator

For intermittent missing data (i.e., for participants with non-missing Week 116 data but missing data at other visits), missing data not associated with an ICE (e.g., for participants who had completed Week 104 visit before protocol v4 was implemented), and for missing data after NSDCR ICEs (handled with a hypothetical strategy), the missing data are assumed to be similar to those from the other participants in the same treatment group with no such missing data. This is compatible with a missing-at-random (MAR) assumption.

All observed data after SDCR ICEs will be included in the analysis. If data after SDCR ICEs are missing, they will be assumed to be similar to those in the placebo group for both study arms. Specifically, data will be imputed based on the placebo arm using reference based imputation with a Copy Increments from Reference (CIR) assumption ([Carpenter et al, 2013](#) and [Cro et al, 2020](#)). This approach appears conservative yet plausible for the study drug. CIR assumes that changes in the primary endpoint after the ICE in a participant randomized to active drug can be represented by, i.e., imputed from, that of participants randomized to placebo. It therefore assumes no treatment effect after the ICE. In the placebo arm, this is compatible with a MAR assumption whereas in the active drug arm, the imputation is under a Missing Not At Random (MNAR) assumption.

Further details about the implementation of the missing data imputation are provided below. Sensitivity analyses for the missing data assumptions are discussed in Section 5.3.4.

Description of the primary estimator

The primary estimator will be applied to the ITT analysis set (see Table 2) and it will be implemented using four steps. First, an imputation model will be fitted to the data. Second, imputation of missing data will be performed based on the parameter estimates from the imputation model. Third, the completed data will be analyzed using an analysis of covariance (ANCOVA) model. Finally, inference will be performed based on resampling techniques. All four steps are described and justified in a published manuscript (Wolbers et al. 2022) which provides a more detailed justification of the statistical methodology and supportive simulations. Considerations about the control of type-I error for the primary estimator and supportive simulations, mimicking the setting of the GRADUATE I and GRADUATE II studies and exploring an extended range of plausible scenarios for missing data, are provided in the Appendix 1.

1. Imputation model

The imputation model is a mixed effects model for repeated measures (MMRM) with the longitudinally assessed change from baseline in CDR-SB as the dependent variable. Its purpose is to estimate mean trajectories and covariance matrices of longitudinal outcomes in the placebo and active drug arms, respectively, while subjects remain on their randomized treatment. Therefore, all data after withdrawal from study treatment will be removed and considered as missing for the purpose of estimating the imputation model, and for this purpose only. If these data were not excluded, then the imputation model would estimate mean trajectories based on a mixture of observed pre- and post-discontinuation data. These would not be compatible with the CIR assumption employed in the subsequent imputation step, which requires combining mean trajectories while on active drug up to the ICE with increments while on placebo thereafter, respectively.

The imputation model includes the following covariates: treatment group, visit, and treatment-by-visit interaction, baseline CDR-SB score and baseline CDR-SB score-by-visit interaction, baseline ADAS-Cog 13 total score, baseline ADCS-ADL total score and the randomization stratification factors, namely: disease stage (from the eCRF), geographic region (from the IxRS), the use of AD medication at baseline (derived from the eCRF based on a search of medications; see below for more details) and the APOE ε4 status (from the Vendor). For geographic region, IxRS is preferred over the eCRF source, to keep the “starting” region for analysis, in case a participant moved to a different region during the study (the eCRF would otherwise reflect the “final” region). AD medication at baseline will be defined as any use of donepezil, galantamine, memantine or rivastigmine prior to randomization and with an

end date not before the randomization date. An unstructured variance-covariance structure will be applied to model the within-subject errors across visits. If the model fails to converge, then a heterogeneous Toeplitz covariance structure will be used instead and if this still fails, then a compound symmetry covariance structure will be used.

Imputations will be based on restricted maximum likelihood (REML) estimation of the regression and covariance parameters from the imputation model ([von Hippel and Bartlett 2021](#); [Wang and Robins 1998](#)).

2. Imputation step

The imputation model implies a marginal multivariate normal distribution of the longitudinal outcome values across all visits based on a participant's assigned treatment arm and covariate values. This marginal imputation distribution will be used for all participants in the placebo arm and all participants in the active drug arm without an SDCR ICE. For participants in the active drug arm with an SDCR ICE, the mean of the marginal imputation distribution for outcomes after the SDCR ICE will be modified as per the CIR assumption ([Carpenter et al. 2013](#)).

For each participant, the conditional imputation distribution of their missing outcome values is defined as the marginal imputation distribution conditional on the participant's observed outcomes (including observed post-SDCR ICE outcome assessments). A single deterministic imputation using the conditional mean from the conditional imputation distribution for each participant with missing outcomes will be used.

3. Analysis step

The completed data (using conditional mean imputation as described above) will be analyzed using an ANCOVA model with the change from baseline in CDR-SB at the Week 116 visit as the dependent variable. This analysis model includes treatment group as the primary covariate with adjustment for the same set of covariates as for the imputation model described above, namely baseline CDR-SB score, baseline ADAS-Cog 13 total score, baseline ADCS-ADL total score and the randomization stratification factors namely: disease stage (from eCRF), geographic region (from the IxRS), the use of AD medication at baseline (derived from eCRF based on a search of medications; see below for more details) and the APOE $\epsilon 4$ status (from the Vendor). For geographic region, IxRS is preferred over the eCRF source, to keep the "starting" region for analysis, in case a participant moved to a different region during the study (the eCRF would otherwise reflect the "final" region). AD medication at baseline will be defined as any use of donepezil, galantamine, memantine or rivastigmine prior to randomization and with an end date not before the randomization date. The primary treatment effect estimator is defined as the regression coefficient associated with the treatment group. The treatment effect will be reported as a difference in adjusted means. The treatment

effect at the other visits will be estimated in the same way and will be reported as supplementary analyses of the primary endpoint (see Section 5.3.5).

Percent relative difference, defined as 100 times the estimated treatment effect divided by *the absolute value of the* placebo arm estimate, will also be reported, for all visits, as a point estimate for descriptive purposes. Importantly, ANCOVA is applied to a complete dataset after appropriate missing data imputation. For complete data, ANCOVA applied to outcomes from a single visit is equivalent to a more complex MMRM model. It can be demonstrated that it leads to identical parameter estimates as a corresponding MMRM model with an arbitrary covariance structure if separate regression coefficients are estimated at different visits for all covariates (Amemiya 1985, p. 197).

4. Inference step

Inference will be based on resampling techniques as recommended by von Hippel and Bartlett 2021. Specifically, the jackknife (Efron and Tibshirani, 1994) will be used to estimate the standard error of the primary treatment effect estimator and the test of the primary statistical hypothesis will be based on the corresponding Z-score. Compared to other resampling techniques, the jackknife has the advantage of providing a deterministic standard error estimate and, hence, removing any simulation randomness from the procedure.

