## 4.2 METHOD OF TREATMENT ASSIGNMENT AND BLINDING

Randomization will be performed centrally using an interactive voice or Web-based response system (IxRS). After screening, participants who meet all eligibility criteria will be randomly assigned to one of two treatment groups (gantenerumab or placebo). The ratio will be 1:1, one active to one placebo. The randomization method will be stratified block-randomization. Randomization to treatment allocation will be stratified by geographic region (Western Europe and Australia vs. Rest of the World vs. North America), participant *APOE*  $\epsilon$ 4 status (carrier vs. non-carrier), participant stage of disease (prodromal vs. mild AD), use of AD medication (present vs. absent), and participation in the longitudinal amyloid and tau PET substudies. Except in circumstances in which a health authority, EC, or IRB requires it, a participant will not be told of his or her *APOE*  $\epsilon$ 4 status. Individual participant *APOE*  $\epsilon$ 4 genotype results will be blinded to participants, investigators, and the Sponsor. *APOE*  $\epsilon$ 4 status information will be supplied directly to the IxRS vendor by the central testing laboratory so that the information can be incorporated at the time of randomization. For participants for whom *APOE*  $\epsilon$ 4 status is already known, the results will be blinded to the Sponsor and as much as possible to the site and central MRI reader.

The study is to be conducted in a double-blind manner to minimize potential bias from investigators and participants. The Sponsor will be blinded to study treatment. Sponsor, participants, and site staff will remain blinded to previous treatment allocation in the OLE period. The Master Randomization or Master Medication List will not be available at the study center, to Roche monitors, Roche project statisticians, or to the project team at Roche. Unblinding should not occur except in the case of emergency situations where knowledge of the study drug assigned would affect participant care. The investigator should make every effort to contact Roche before unblinding a participant. In the event that the investigator unblinds a participant without prior notification, the investigator must contact Roche within 1 working day of the event. Any request from the investigator for information about the treatment administered to study participants for another purpose must be discussed with the Medical Monitor.

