1.2 STUDY DESIGN

GRADUATE I and GRADUATE II are two identical Phase III, multicenter, randomized, double-blind, placebo-controlled, parallel-group studies designed to evaluate the efficacy and safety of gantenerumab in participants with early (prodromal to mild) AD.

The planned number of participants for the global enrollment phase for each study is approximately 1016 participants randomized in a 1:1 ratio to receive active drug or placebo (508 participants randomized to active drug and 508 randomized to placebo; see Section 3). To maintain a balanced number of participants enrolled in each treatment arm and to ensure that the arms are comparable, randomization will be stratified by stage of the disease (prodromal AD vs. mild AD), apolipoprotein ϵ 4 (APOE) allele status (presence vs. absence of the ϵ 4 allele), use of AD medication (presence vs. absence), geographic region (Western Europe and Australia vs. Rest of the World vs. North America), and participation in the longitudinal amyloid and tau PET substudies. Approximately 175 centers in approximately 15 countries worldwide will participate in these studies.

Due to the global impact of the coronavirus disease (COVID-19) pandemic and the resulting disruption in study drug administration, the duration of the double-blind treatment period was extended by 12 weeks, with Protocol Amendment 4. The optional scenario of a further extension of 12 weeks – resulting in a final efficacy and safety visit at Week 128 – was not implemented. An overview of the study design is provided in [Figure 1](#).

Figure 1 Overall Study Design

Each study consists of three distinct periods:

Screening (including an optional prescreening): The screening period may last up to 12 weeks for each eligible participant.

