1.2.1 Treatment Assignment and Blinding

Randomization will be performed centrally using an interactive voice or Web-based response system (IxRS). After screening, participants who meet all eligibility criteria will be randomly assigned to one of two treatment groups (active drug or placebo). The ratio will be 1:1; one active to one placebo. The randomization method will be stratified block-randomization. Randomization to treatment allocation will be stratified by geographic region (Western Europe and Australia vs. Rest of the World vs. North America), participant APOE ϵ 4 status (carrier vs. non-carrier), participant stage of disease (prodromal vs. mild AD), use of AD medication (presence vs. absence), and participation in the longitudinal amyloid and tau PET substudies. Except in circumstances in which a Health Authority, Ethics Committee, or Institutional Review Board requires it, a participant will not be told of his or her APOE ϵ 4 status. Individual participant APOE ϵ 4 genotype results will be blinded to participants, Investigators, and the Sponsor. APOE ϵ 4 status information will be supplied directly to the IxRS vendor by the central testing laboratory so that the information can be incorporated at the time of randomization. For participants for whom APOE ϵ 4 status is already known, the results will be blinded to the Sponsor and, as much as possible, to the site and central MRI reader.

The study is to be conducted in a double-blind manner to minimize potential bias from Investigators and participants. The Sponsor will be blinded to study treatment. In the OLE phase, the Sponsor, participants, and site staff will remain blinded to previous treatment allocation.

The randomization method implemented in the China extension cohort will be the same as that implemented in the global population.

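### The primary models claim to adjust for the randomisation stratification factors but name four of the five, leaving out PET-substudy participation

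*SAP*

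**What the plan says.** Both documents give the same five stratification factors. Protocol 4.2 lists region, APOE ε4 status and disease stage, then "use of AD medication (present vs. absent), and participation in the longitudinal amyloid and tau PET substudies". SAP 1.2.1 matches it, closing with "use of AD medication (presence vs. absence), and participation in the longitudinal amyloid and tau PET substudies", and gives the method: "The randomization method will be stratified block-randomization". Protocol 3.1.1 and SAP 1.2 carry the same five.

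SAP 5.3.3 then describes the covariates. Step 1, the imputation model, adjusts for "the randomization stratification factors, namely: disease stage (from the eCRF), geographic region (from the IxRS), the use of AD medication at baseline" and APOE ε4 status. Step 3, the ANCOVA, adjusts for "the randomization stratification factors namely: disease stage (from eCRF), geographic region (from the IxRS), the use of AD medication at baseline" and APOE ε4 status. PET-substudy participation appears in neither.

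The four-factor list recurs in the supplementary MMRM (SAP 5.3.5.2), the secondary endpoints (SAP 5.4) and the exploratory endpoints (SAP 5.5). SAP 5.4.1 points back to the primary endpoint's factors for its own MMRM.

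**The concern.** The wording presents the list as the full set of stratification factors, and it is not. A programmer could follow the description (five) or the list (four), and a report that the model adjusted for the stratification factors would be inaccurate.

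There is also a statistical consequence. Blocking within PET strata balances the arms on that factor, which lowers the true variance of the treatment difference if the factor is prognostic. A model without the factor leaves its contribution in the residual, so the reported standard error does not reflect the gain. The jackknife does not help: it removes participants one at a time and gives no credit for balance achieved by blocking. Where final blocks are incomplete, any chance imbalance on the factor also goes uncorrected.

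This is the covariate set of the one analysis that can reject the primary null hypothesis (SAP 5.8), so it should be exact.

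**Working it through.** **1. Factor count**

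| Factor | Randomisation (Protocol 4.2, SAP 1.2.1) | Models (SAP 5.3.3, steps 1 and 3) |
|---|---|---|
| Disease stage | yes | yes, from the eCRF |
| Region | yes | yes, from the IxRS |
| AD medication | yes | yes, derived from the eCRF |
| APOE ε4 status | yes | yes, from the vendor |
| PET-substudy participation | yes | **no** |

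**2. The plan's own figure.** SAP 3 assumes a placebo change of 2.5, SD 2.97, a 30% reduction, 90% power and two-sided α of 0.05. The difference is 0.30 × 2.5 = 0.75. The normal approximation gives 2 × (1.960 + 1.282)² × 2.97² / 0.75² = 329.5, so 330 per arm and 660 in total. Then 660 / 0.65 = 1015.4, which rounds up to the stated 1016. (The t-test version gives 331 per arm, about 1018.) This calculation uses no covariates, so the sample size does not depend on the omitted factor.

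**3. Variance left in the residual.** Let *p* be the share in a PET substudy and *d* the difference in mean CDR-SB change between participants and others. Neither is in the documents; both are assumed. With 1:1 balance on the factor:

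- share of variance left in: f = p(1 − p)d² / SD²
- reported SE over true SE: 1 / √(1 − f)
- actual two-sided type I error: 2[1 − Φ(1.960 / √(1 − f))]

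With SD² = 2.97² = 8.82:

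| p | d | f | SE too large by |
|---|---|---|---|
| 0.2 | 0.3 | 0.0144 / 8.82 = 0.2% | 0.1% |
| 0.2 | 0.5 | 0.0400 / 8.82 = 0.5% | 0.2% |
| 0.4 | 1.0 | 0.2400 / 8.82 = 2.7% | 1.4% |

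Over p = 0.10 to 0.50 and d = 0.25 to 1.0, type I error with the factor omitted runs from 0.0499 down to 0.0468. At 660 effective participants, power is 90.1% to 90.4% with the factor omitted and 90.1% to 90.8% with it included, a gain of at most 0.5 percentage points.

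**4. A smaller residual SD.** The models adjust for baseline, so 2.97 is probably too large a denominator. SAP Appendix 1 simulates a Week 116 variance of 4.26 and a correlation of 0.52 with baseline, giving a residual variance of 4.26 × (1 − 0.52²) = 3.11. Here *d* means the difference remaining after adjustment:

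- p = 0.2, d = 0.5: f = 0.04 / 3.11 = 1.3%, SE about 0.6% too large
- p = 0.4, d = 1.0: f = 0.24 / 3.11 = 7.7%, SE about 4% too large, type I error about 0.041

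These figures assume complete balance on the factor. Incomplete blocks would reduce the conservatism and put some avoidable noise into the estimate instead.

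**The case against.** The effect may be negligible. The larger figures need a 1.0-point difference, which is 40% of the whole assumed placebo decline of 2.5 points, and nothing in the documents says that substudy participation is prognostic. Only the difference remaining after baseline CDR-SB, ADAS-Cog 13, ADCS-ADL, stage, region, medication and APOE matters, and some of it may overlap with region, since tracer use depends on country and site (SAP 5.7.5). That stands as a point about size: the first two rows of the table are more plausible than the third. It does not change the direction.

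The SAP also does not try to reproduce the IxRS strata, since only region comes from that source, and the same four factors are used throughout, so an analyst following the list has no freedom. That too is fair, but a form of each of the other four factors is in the model, whereas nothing represents the fifth.

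Finally, the levels of the PET factor are not defined (yes/no, or amyloid and tau separately), and SAP Table 2 allows for withdrawal from a substudy before randomisation. Taking the levels as coded in the IxRS stratum settles both: the factor to adjust for is the one used to randomise. The alternative of listing four factors as a stated subset, with a reason, would remove the contradiction but not the loss of precision.

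**Conclusion.** The concern holds. Five factors restrict the randomisation and four are adjusted for, under wording that claims all of them, with no reason given.

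It does not threaten validity: the estimate is unbiased, type I error stays at or below 5%, and the sample size is unaffected. With the planning SD, the standard error is between a negligible amount and about 1.4% too large for the cases tabulated; with the smaller residual variance implied by Appendix 1, the extreme case reaches about 4%. All these sizes rest on assumed values of *p* and *d* and on balance within PET strata. The change should be made because it corrects the specification of the primary test and can only help its precision to any material degree.

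**What to change.** Add PET-substudy participation, taken from the IxRS stratum with the levels used for randomisation, to the factor lists in:

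- SAP 5.3.3, step 1 (imputation model) and step 3 (ANCOVA)
- SAP 5.3.5.2, supplementary MMRM
- SAP 5.4, 5.4.1 and 5.5, secondary and exploratory models

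State the levels once in 5.3.3 so that the other sections can refer to them.

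The cost is a phrase in each place and one covariate: one extra main-effect parameter if coded yes/no, up to three if coded in four levels. SAP 5.7.1 already plans to summarise the stratification factors held in the IxRS, so no new data are needed. If the imputation model fails to converge, SAP 5.3.6 already allows covariates to be dropped or levels pooled. At about 1,016 participants the loss of degrees of freedom is immaterial.
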